#### **Handling of missing data:**

Missing data will not be imputed, i.e. only observed data will be used.

# 7 Definition of Endpoints

## 7.1 Safety Endpoints

Following are the study's safety endpoints:

- Treatment-emergent adverse events (TEAEs), including serious adverse events (SAEs)
- Infusion reactions
- Physical examination
- Vital signs (blood pressure, heart rate, temperature and respiratory rate)
- ECG
- Concomitant medications

• Laboratory evaluation (hematology, biochemistry, anti-bertilimumab antibodies).

## 7.2 Primary Efficacy Endpoints

Clinical response at Day 56 (Visit 7), defined as:

"Success" ('1')	A decrease from the pre-treatment screening total
	Mayo score of at least 3 points and at least 30%
	AND
	Either a decrease from the pre-treatment screening sub-score for rectal bleeding of at least 1 point, or
	Rectal Bleeding Sub-score of 0 or 1.
"Failure" ('0')	Otherwise

## 7.3 Secondary Efficacy Endpoints

- Change in Mayo Score from screening to Day 56 (Visit 7), calculated as
  - Change in Mayo Score = Mayo Score at Screening Mayo Score at Day 56
- Change in UCEIS score from screening to Day 56 (Visit 7), calculated as
  - Change in UCEIS score = UCEIS score at Screening UCEIS score at Day 56
- Clinical remission at Day 56 will be defined as
  - Success "1", if total Mayo score of 2 points or lower, with no relevant individual sub-score exceeding 1 point.
  - o Failure "0", otherwise.
- Mucosal healing at Day 56 will be defined as
  - O Success "1", if absolute sub-score for endoscopy of 0 or 1.
  - o Failure "0", otherwise.
- Change in partial Mayo score from Day 0 to all scheduled measurement timepoints (efficacy follow up) calculated as
  - Change in partial Mayo score = Partial Mayo score at Screening –
    partial Mayo score at Visit t

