	At Visit 2, inclusion and exclusion criteria will be reviewed. The following assessments will be performed at each treatment visit pre-dose : physical examination, vital signs, ECG, partial Mayo score, eosinophil count, serum eotaxin-1, high-sensitivity C-reactive protein (hs-CRP), eosinophil cationic protein (ECP), pre-dose blood samples for PK (bertilimumab concentration), calprotectin in fecal samples, urine pregnancy test (for females of childbearing potential) and safety laboratory evaluations (hematology, biochemistry, antibodies to bertilimumab). A regimen for infusion reaction prophylaxis, described below (see section "Prophylaxis for Prevention of Infusion Reaction"), will be administered.
	At each treatment visit, following completion of the pre-dose assessments, and administration of the pre-treatment regimen according to the timeframes noted, bertilimumab/matching placebo will be administered by IV infusion over 30 minutes. Vital signs will be recorded at 15 minutes (during infusion), 30 (+15) minutes (immediately post infusion), 2 hr (±20 minutes) and 4 hr (±20 minutes) following initiation of study drug infusion. ECG will be performed at 30 (+15) minutes (immediately post infusion). Blood samples for bertilimumab concentration (PK analysis) will be collected 30 (+15) minutes and 4 hours (±20 minutes) following initiation of study drug infusion. I Adverse events (AE) and concomitant medications will be recorded.
	Follow-Up Period ^d – Visit 5 (Day 35), Visit 6 (Day 42), Visit 7 (Day 56) and Visit 8 (Day 90)
	The following assessments will be performed at the follow-up visits: physical examination, vital signs, ECG, AE and concomitant medication recording, partial Mayo score (Visits 5, 6 and 8), safety laboratory evaluations (hematology, biochemistry, antibodies to bertilimumab), blood samplescollection for bertilimumab concentration (PK analysis), ECP, eosinophil count, serum eotaxin-1 and hs-CRP. Calprotectin will be evaluated in fecal samples. Visit 7 (Day 56) will also include flexible sigmoidoscopy with biopsies, and evaluation of UCEIS, Mayo score, eotaxin-1 and eosinophil count in tissue samples.
Study Duration	Study duration for each subject will be approximately 118 days \pm 12 days (\sim 16-19 weeks) as follows:
	Screening period: Up to 28 days
	Treatment period: 28 days (±3 days)
	Follow-up period: 62 days (±9 days)

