2.2 STUDY ENDPOINTS AND OUTCOMES

2.2.1 Efficacy Endpoints

Primary

• Change in Mayo Score from screening to Day 56 (Visit 7). Clinical response at Day 56g will be defined as:

0	A decrease from the pre-treatment screening Mayo score of at least 3 points
	and at least 30%

AND

Protocol: Immune/BRT/UC-01 Page 20 of 58

^f In this protocol, "study drug" refers to either bertilimumab or placebo.

^g This and all other follow-up visits have a window of ± 3 days.

• Either a decrease from the pre-treatment screening sub-score for rectal bleeding of at least 1 point, or Rectal Bleeding Sub-score of 0 or 1.

Secondary

- Change in UCEIS score from screening to Day 56.
- Clinical remission at Day 56, defined as a total Mayo score of 2 points or lower, with no individual sub-score exceeding 1 point.
- Mucosal healing at Day 56, defined as an absolute sub-score for endoscopy of 0 or 1.
- Change in partial Mayo score from Day 0 to all scheduled measurement timepoints (efficacy follow up).

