5.1 SCREENING PERIOD (VISIT 1, DAY -28 TO DAY -1)

The purpose and procedures of the study will be fully explained to participating subjects. Those wishing to enroll in the study will sign a written informed consent prior to initiating any study related evaluations or procedures.

The following assessments will be done at the screening visit, up to 28 days before initiation of treatment (Day 0):

- Review and sign Informed Consent
- Assign screening number
- Inclusion and Exclusion Criteria
- Medical history and demographic data
- Prior and concomitant medications
- Physical examination (including vital signs, height and weight measurements)
- ECG
- Screen for active/latent tuberculosis (Interferon Gamma Release Assay)
- Screen for *C. Difficile* toxin in stool sample
- Flexible sigmoidoscopy with biopsies. At least 3 tissue samples are required from area of active inflammation. Additional biopsy samples may be obtained at the Investigator's discretion for histological assessment.
- Mayo score
- UCEIS
- Eotaxin-1 in tissue will be measured using two of the biopsy samples
- Eosinophil count in tissue will be measured histologically using the remaining biopsy sample
- Calprotectin in fecal sample
- Laboratory evaluations: hematology, biochemistry, serology and serum pregnancy test for females of childbearing potential.
- Eligible subjects will be randomized in a 2:1 ratio to one of two treatment arms, bertilimumab 10 mg/kg or matching placebo.

The screening visit may be conducted over multiple days. Screening visit data (Mayo score, UCEIS, eotaxin-1 and eosinophil count in tissue sample) will be considered baseline data for statistical analysis purposes.

5.2 TREATMENT PERIODⁱ: VISIT 2 (DAY 0), VISIT 3 (DAY 14) AND VISIT 4 (DAY 28)

At Visit 2 (Day 0), inclusion exclusion criteria will be reviewed.

The following assessments will be performed at each treatment visit (Day 0, Day 14 and Day 28) pre-dose:

- Physical examination
- Vital signs
- ECG
- Partial Mayo score
- Safety laboratory evaluations: hematology, biochemistry, antibodies to bertilimumab.
- Blood samples for eosinophil count^j, serum eotaxin-1, hs-CRP^k and ECP

Protocol: Immune/BRT/UC-01

Page 26 of 58 Final Version 8.0 May 23, 2018

ⁱ Visits 3 and 4 during the Treatment Period have a ± 2 day window.

^j Done using the hematology blood sample.

^k Done using the biochemistry blood sample.

- Blood samples for bertilimumab (PK analysis)
- Calprotectin in fecal samples

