5.7.2 Mayo score

The Mayo Scoring System (Appendix B) for assessment of UC activity will be used for efficacy evaluation. The score will be determined at Screening (Visit 1) and Day 56 (Visit 7).

The Mayo Score is a discrete ordinal scale ranging from 0 (normal or inactive disease) to 12 (severe disease) and is a composite of 4 sub-scores: Stool Frequency Sub-score, Rectal Bleeding Sub-score, Endoscopic Finding Sub-score and Physician's Global Assessment Sub-score, each of which ranges from 0 (normal) to 3 (severe disease) [18]. The sub-scores are summed to give a total score that ranges from 0–12.

The partial Mayo Score is a 9-point scale that excludes the Endoscopic Finding Sub-score. It will be used for assessment of disease activity on Day 0 (Visit 2), Day 14 (Visit 3), Day 28 (Visit 4), Day 35 (Visit 5), Day 42 (Visit 6) and Day 90 (Visit 8).

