Appendix A Schedule of Activities

Protocol: Immune/BRT/UC-01 Page 53 of 58 Final Version 8.0 May 23, 2018

Study Procedures	Screening Period	Tr	eatment Pe	riod ^a	Early Discontinuation ^b	Follow-up Period ^c			
Visit	1	2	3	4	-	5	6	7	8
Study Day	-28 to -1	0	14	28	-	35	42	56	90
Inclusion/exclusion criteria	X	X							
Informed consent	X								
Demographic & medical history	X								
Physical examination	X	X^*	X*	X*	X	X	X	X	X
Vital signs	X	X^d	X ^d	X ^d	X	X	X	X	X
ECG	X	Xe	Xe	Xe	X	X	X	X	X
Screen for active/latent tuberculosis and fecal sample for C. difficile toxin	X								
Randomization	X								
Mayo Score	X				X			X	
Partial Mayo Score	X	X^*	X*	X*	X	X	X	X	X
Bertilimumab or Placebo infusion- (after administration of pretreatment regimen) ^j		X	X	X					
Flexible sigmoidoscopy with biopsies ^f	X				X			X	
Ulcerative Colitis Endoscopic Index of Severity	X				X			X	
Adverse events		X	X	X	X	X	X	X	X
Concomitant medications	X	X	X	X	X	X	X	X	X
Infusion reaction assessment ^g		X	X	X					
Urine β-hCG		X^*	X*	X*					
Hematology and biochemistry	X ^h	X*	X*	X*	X	X	X	X	X
Serology	X								
PK (bertilimumab) blood sampling		Xi	Xi	Xi	X	X	X	X	X
Anti-bertilimumab antibodies		X*	X*	X*	X	X	X	X	X
Eotaxin-1, eosinophil count, eosinophil cationic protein (ECP)-s-CRP		X*	X*	X*	X	X	X	X	X

^a Visits during the treatment period have a ± 2 day window.

Protocol: Immune/BRT/UC-01 Page 54 of 58 Final Version 8.0 May 23, 2018

^b At this visit the activities relating to the study period at which time the patient discontinued will be performed.

^c Visits during the follow-up period have a ± 3 day window.

d Vital signs will be measured pre-dose and 15 min (during), 30 minutes (+15 minutes), 2 hr (± 20 minutes), and 4 hr (± 20 minutes) following initiation of study drug administration.

^e ECG will be performed pre-dose, and at 30 (+ 15) minutes following initiation of study drug administration.

f At least 3 tissue samples are required from area of active inflammation at Screening. On Day 56 (or early discontinuation visit), at least 3 tissue samples are required from the same region where Screening biopsies were obtained. Additional biopsy samples may be collected at the Investigator's discretion for histological assessment.

g Infusion reactions will be monitored for up to 4 hours following study drug administration and graded, as applicable, as appears in Appendix D

^h Biochemistry will include serum β-hCG at screening.

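### SAP 7.3 defines the partial Mayo endpoint as change from Day 0, but its formula starts from the Screening score

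*SAP*

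**What the plan says.** The SAP 7.3 bullet names the endpoint: "Change in partial Mayo score from Day 0 to all scheduled measurement timepoints". The formula directly under it reads "Change in partial Mayo score = Partial Mayo score at Screening", less the partial Mayo score at Visit t.

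Protocol 2.2.1 gives the same reference as the SAP label: "Change in partial Mayo score from Day 0 to all scheduled measurement timepoints (efficacy follow up". The synopsis agrees.

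Both scores exist:

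- **Day 0.** The protocol synopsis includes the partial Mayo score among the pre-dose assessments at each treatment visit. Protocol 5.2 does the same, under "The following assessments will be performed at each treatment visit (Day 0, Day 14 and Day 28". Protocol 5.7.2 says of the partial score: "It will be used for assessment of disease activity on Day 0 (Visit 2", followed by the later visits. Both schedules mark it pre-dose at Visit 2.
- **Screening.** Both schedules also mark a Screening partial Mayo, and SAP Table 1 footnote 11 derives it from the total score.

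Protocol 5.1 names the measures whose baseline is Screening: "Screening visit data (Mayo score, UCEIS, eotaxin-1 and eosinophil count in tissue sample) will be considered baseline data for statistical analysis purposes". Partial Mayo is not among them.

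**The concern.** Screening (Visit 1, Day -28 to -1) and Day 0 (Visit 2) are different visits. Read as a derivation rule, the formula does not compute the endpoint that the bullet and the protocol define. SAP 9.4.2 asks for descriptive statistics of the change by visit and arm without giving a start point, so it relies on the contradictory text in 7.3.

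A programmer who follows the label and one who follows the formula would produce different tables. If the formula is followed, the mean, SD, median and range presented for this endpoint include change that occurred before the first infusion.

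**Working it through.** No figure in the plan needs reproducing. The check compares the passages, applies one identity, and gives the size under stated assumptions.

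**1. Consistency test.** Set t = Visit 2. A change from Day 0 must then be zero for every subject. The SAP formula gives Screening minus Day 0, which need not be zero. Label and formula cannot both be right.

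**2. Size of the discrepancy.** With S, D and V for the partial Mayo at Screening, Day 0 and Visit t:

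(S - V) = (D - V) + (S - D)

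The two definitions differ by (S - D) for each subject, by the same amount at every visit. Hypothetical example: S = 7, D = 5, V = 4 gives 7 - 4 = 3 by the formula and 5 - 4 = 1 by the label. At arm level, a mean fall of 1 point from Screening to Day 0 adds exactly 1 point to that arm's mean improvement.

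**3. Can the direction be predicted?** Protocol 4.1 requires, at Screening, rectal bleeding of at least 1, PGA of at least 2, endoscopy of at least 2 and a total of 6 to 12. The lowest possible Screening partial Mayo is 0 + 1 + 2 = 3 (stool frequency, bleeding, PGA), which needs endoscopy 3 to reach a total of 6. The highest is 9. These thresholds are worded for the screening visit. Selection on the Screening value makes some fall by Day 0 through regression to the mean plausible, but the documents give no data on its size or direction.

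**4. Effect on the comparison of arms.** Randomization takes place in the screening period and both scores precede study drug, so the expected (S - D) is the same in both arms and the expected difference is not biased. The realised difference still moves by chance. Assume 42 subjects split 28:14, complete data, and a common SD of (S - D):

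- difference between arms: SE = SD x sqrt(1/28 + 1/14) = 0.327 x SD
- active arm mean: SE = SD x sqrt(1/28) = 0.189 x SD
- placebo arm mean: SE = SD x sqrt(1/14) = 0.267 x SD

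| Assumed SD of (S - D) | SE of shift in arm difference (points) |
|---|---|
| 0.5 | 0.16 |
| 1.0 | 0.33 |
| 1.5 | 0.49 |
| 2.0 | 0.65 |

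The SDs are assumptions; the documents give none.

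**5. What can be recovered.** SAP 9.4.2 also tabulates the raw partial Mayo by visit. With complete data, mean D minus mean V gives the Day 0-based mean change. The SD, median and range of that change do not follow from the planned tables and would have to be recalculated from the subject listings (SAP 10).

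**6. Does another passage settle the reference?** The general rule in SAP 8 takes the latest value before treatment, which points to Day 0. It is supporting evidence only: a specific formula could override it, and SAP 9.3 uses change from Screening for vital signs and ECG. SAP 7.5 does show that the authors distinguish the two visits, with Day 0 as baseline for calprotectin and the blood markers and Screening for the tissue measures.

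**The case against.** The strongest counter-argument is that Screening may have been intended. SAP footnote 11 sets out how to derive a Screening partial Mayo, which looks deliberate. The protocol's version 8.0 change log says UCEIS and Mayo scores are compared with screening. Protocol 5.1 makes the Screening Mayo score a baseline, and the partial score comes from the same assessment. The absence of a declared departure proves little, because the SAP changes other protocol rules, such as the mITT definition, without saying so.

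This explains how the formula could have arisen but does not resolve the conflict. The footnote makes the Screening value computable; it does not make it the reference. The log is a summary, and the version 8.0 endpoint text still gives Day 0 for partial Mayo.

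Other points stand in part:

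- If the tables include a Visit 2 row, the pre-drug shift would be visible. It would still not be removed from the later rows.
- Eligibility is reviewed again at Visit 2, so one cannot say flatly that Day 0 scores have no floor. The criterion is worded for the screening visit, however, and the text does not say that the sub-score thresholds are re-applied.
- Day 0 is not a uniform reference. For subjects premedicated under version 8.0, the pre-dose score can follow the oral dexamethasone given 18 to 24 hours before infusion. SAP 6.1 notes that the prophylaxis requirement came in with that version. This affects both arms, and it is a reason to state the reference precisely.
- The endpoint is descriptive and secondary in an exploratory trial, which limits the consequence.

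**Conclusion.** The contradiction is certain: the SAP formula does not compute the endpoint named in its own bullet and in protocol 2.2.1. Followed as written, it misses that endpoint by (Screening minus Day 0) for each subject at every visit.

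The practical size is unknown, because the documents give neither the mean nor the SD of that difference. The SEs of 0.16 to 0.65 points rest on assumed SDs of 0.5 to 2.0, equal SDs in the arms, full recruitment to 42 with an exact 2:1 split, and complete data. They describe chance movement between two unbiased contrasts.

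The primary endpoint is unaffected; both documents measure it from Screening. This should be corrected, but it does not threaten the trial's main conclusion.

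**What to change.** In SAP 7.3, replace the formula with: change = partial Mayo at Day 0 (Visit 2, pre-dose) minus partial Mayo at Visit t, for visits after Day 0. State that Day 0 means before the first study-drug infusion, since the score may follow premedication.

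Add a rule for a missing Day 0 score. One option is the Screening value, as the latest pre-treatment measurement under SAP 8. That fallback would be a SAP choice with no basis in a protocol rule, so subjects who rely on it should be flagged.

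If Screening is the intended reference, relabel the endpoint as change from Screening, declare the departure from protocol 2.2.1, and give the Day 0 version as supplementary.

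The cost is one SAP line, the short missing-data rule and one derivation from data already collected. If scores fell between Screening and Day 0, the per-arm improvement will look smaller than under the current formula.

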## 7.4 Pharmacokinetics (PK) Endpoints

Blood samples will be collected on dosing days (pre-dose and at 30 minutes ( $\pm$  15 minutes) and 4 hours ( $\pm$ 20 minutes) following the initiation of study drug infusion) and at the follow-up visits. The following PK parameters will be calculated:  $C_{max}$ ,  $T_{max}$ ,  $C_{avg}$ ,  $C_{min}$ , and  $t_{1/2}$ . Additional standard and exploratory PK parameters will be calculated if deemed necessary.

## 7.5 Pharmacodynamic (PD) Endpoints

- Fecal calprotectin change from Day 0 (baseline) to all scheduled measurement timepoints.
- Change in eosinophil count, serum eotaxin-1, hs-CRP and ECP from Day 0 to all scheduled measurement timepoints.
- Change in eotaxin-1 concentration and max and mean eosinophil count in biopsy tissue from Screening to Day 56.

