For numeric continuous endpoints: Descriptive statistics and summary tables will include sample size, arithmetic mean, standard deviation, median, minimum and maximum, and 95% Confidence Interval (CI) for mean at the relevant time points by treatment and placebo corrected for the active treatment group.

For ordered categories endpoints: incidences in the different categories and, after dichotomization into success/failure-like categories, incidence of failure and relative risk of failure in the active group towards placebo with 95% confidence intervals.

This is an exploratory trial whose main analyses will be descriptive in nature. Where statistical testing will be applied, an alpha of 0.1 will be considered significant. At the same time, this being an exploratory trial, there will be no correction for overall Type I Error. The data will be analyzed using the SAS® 9.1 (or higher) software package (SAS Institute, Cary, North Carolina).

Safety Endpoint Analysis

Safety endpoint analysis will be descriptive in nature and done on the safety anlysis set.

Effiacy Endpoints Analysis

Analysis of all efficacy endpoints will be performed on the mITT set. The PP set will be used as supplementary analyses to test the robustness of the results.

TABLE OF CONTENTS

			NATURE PAGE		
PR	OTO	COL VEI	RSION HISTORY	3	
PR	OTO	COL SYN	NOPSIS	7	
TA	BLE	OF CON	TENTS	13	
GL	OSSA	RY		16	
1.			TION		
1.			TIVE COLITIS		
	1.1	1.1.1	The Role of Eotaxin and Eosinophils in Inflammatory Bowel Disease		
	1.2		GATIONAL THERAPY		
		1.2.1	Nonclinical Studies		
		1.2.2	Clinical Studies		
	1.3	STUDY F	RATIONALE	19	
		1.3.1	Rationale for Dose Selection	19	
		1.3.2	Allergic and Infusion Reactions	20	
2.	STU	JDY OBJ	ECTIVES AND ENDPOINTS	20	
	2.1	STUDY (Objectives	20	
	2.2	STUDY E	ENDPOINTS AND OUTCOMES	20	
		2.2.1	Efficacy Endpoints		
		2.2.2	Pharmacokinetic Endpoints		
		2.2.3	Pharmacodynamic Endpoints		
		2.2.4	Safety Endpoints		
3.	STU	JDY DES	IGN	21	
4.	STU	JDY POP	ULATION	22	
	4.1	INCLUSION	on Criteria	22	
	4.2	EXCLUS	ION CRITERIA	22	
	4.3		IDENTIFICATION AND TREATMENT ALLOCATION		
	4.4	SCREEN	ING FAILURES	24	
	4.5	· · · · · · · · · · · · · · · · · · ·			
		ASSESSN	MENT		
		4.5.1	Handling of Early Discontinuation.		
		4.5.2	Adverse Events		
	4.6	SPONSOI	R'S TERMINATION OF STUDY	25	
5.	STU		OCEDURES AND ASSESSMENTS		
	5.1		ING PERIOD (VISIT 1, DAY -28 TO DAY -1)		
	5.2		ENT PERIOD: VISIT 2 (DAY 0), VISIT 3 (DAY 14) AND VISIT 4 (DAY 28)		

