4.1 INCLUSION CRITERIA

- 1. Males or females, 18 to 70 years of age inclusive.
- 2. Diagnosed with active moderate to severe UC per standard diagnostic criteria for a minimum of 3 months. The subject must present with the following at the screening visit:
 - Mayo score of 6-12 (inclusive).
 - Endoscopic evidence of active mucosal disease, as assessed by flexible sigmoidoscopy, with an Endoscopic Finding Sub-score of ≥2 (assessed centrally).
 - Rectal Bleeding Sub-score of ≥1.
 - Physician's Global Assessment (PGA) Sub-score of ≥2.
- 3. Levels of eotaxin-1 in biopsied colon tissue of ≥50 pg/mg protein.
- 4. Adequate cardiac, renal and hepatic function as determined by the Investigator and demonstrated by screening laboratory evaluations and physical examination results; these findings must all be within normal limits or judged not clinically significant by the Investigator.
- 5. Females of childbearing potential must agree to use effective contraception consistently throughout the study (such as hormonal contraception or two forms of barrier contraception) and have a negative serum pregnancy test at screening and a negative urine pregnancy test before administration of each study treatment.
- 6. Males of childbearing potential must agree to use effective contraception consistently throughout the study and a period of four months following the end of the study treatment-
- 7. Willing and able to adhere to the study visit schedule and other protocol requirements.
- 8. Willing and able to provide voluntary written informed consent.

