5.7 EFFICACY ASSESSMENTS

5.7.1 Sigmoidoscopy

Flexible sigmoidoscopy with biopsies will be performed at Screening (Visit 1) and Day 56 (Visit 7) or early discontinuation visit. At least 3 tissue samples are required from an area of active inflammation at Screening. On Day 56 (or early discontinuation visit), at least 3 tissue samples are required from the same region where Screening biopsies were obtained.

Additional biopsy samples may be collected at the Investigator's discretion for histological assessment.

The Endoscopic Finding Sub-score grading is provided in Appendix B. The UCEIS grading is provided in Appendix C. Each site will perform sigmoidoscopy at Screening (Visit 1) to evaluate eligibility (see Inclusion/Exclusion criteria). For efficacy evaluation, all endoscopic images (Visits 1 and 7 [or early discontuation visit]) will be reviewed centrally according to the procedure provided by the Institution conducting the central reading.

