## 9.4.2 Secondary Efficacy Analysis

Secondary efficacy analysis will be conducted on mITT and PP populations.

- Primary analysis will be repeated using a 95% exact binomial confidence interval.
- Primary analysis will be repeated on PP population and with both 90% and 95% exact binomial confidence intervals.
- Frequency distribution of patient who had UCEIS assessments by visit and treatment group.
- Descriptive statistics of UCEIS score (Vascular pattern, Bleeding, Erosions & Ulcers and total score) by visit, treatment group.
- Descriptive statistics of change in UCEIS score (Vascular pattern, Bleeding, Erosions & Ulcers and total score) from screening to Day 56 (visit 7) by treatment group.
- Frequency distribution of dichotomous clinical remission at Day 56 (Visit 7) as defined in section 7.3.
- Frequency distribution of dichotomous mucosal healing at Day 56 (Visit 7) as defined in section 7.3.
- Descriptive statistics of partial Mayo score (Stool Frequency, Rectal Bleeding, Physician's Global Assessment and total of these sub-scores) by visit and treatment group.
- Descriptive statistics of change in partial Mayo score by visit and treatment group.

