## 9.4.4 Pharmacodynamics (PD)

• Descriptive statistics of PD parameters as described in section 7.5 by visit, time point and treatment group.

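### Tissue eotaxin-1 is both an entry gate and the baseline of its own change endpoint, and the SAP reports that change only within each arm, with no placebo-corrected or baseline-adjusted estimate

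*SAP*

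**What the plan says.** Inclusion criterion 3 (Protocol 4.1) requires "Levels of eotaxin-1 in biopsied colon tissue of ≥50 pg/mg protein". Protocol 5.7.1 fixes where that tissue comes from: "At least 3 tissue samples are required from an area of active inflammation at Screening". Protocol 5.1 then makes the same reading the baseline: "Screening visit data (Mayo score, UCEIS, eotaxin-1 and eosinophil count in tissue sample) will be considered baseline data for statistical analysis purposes". The schedule in Appendix A has no second biopsy before treatment, so the SAP 8 rule (last value before treatment) leads to the same reading.

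The endpoint in SAP 7.5 is "Change in eotaxin-1 concentration and max and mean eosinophil count in biopsy tissue from Screening to Day 56". Its whole analysis, in SAP 9.4.4, is "Descriptive statistics of PD parameters as described in section 7.5 by visit, time point and treatment group". SAP 9 lists the summaries for numerical variables as mean, SD, minimum, median, maximum and count. It names no confidence interval and no difference between arms. SAP 9.4.2 treats change in UCEIS the same way, by arm.

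The protocol synopsis goes further for continuous endpoints, promising a "95% Confidence Interval (CI) for mean at the relevant time points by treatment and placebo corrected for the active treatment group". Protocol 8.3 keeps the interval by treatment but not the placebo correction, and the SAP carries neither into the PD or UCEIS analyses. SAP 9.4.5 lists screening UCEIS and screening tissue eotaxin-1 as covariates, but its stated output is the primary endpoint by covariate level.

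**The concern.** A subject enters only if the screening reading is high enough. Part of any high reading is assay and sampling variation, which is not expected to recur at Day 56. The later value is therefore expected to be lower on average, with or without drug. Taking the screening tissue from inflamed mucosa pushes in the same direction.

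Bertilimumab neutralises eotaxin-1, and Protocol 1.3.1 groups tissue eotaxin with the markers of drug activity and plans to relate it to therapeutic response. A fall in the bertilimumab arm invites reading as target engagement. If the only table shows change within each arm, nothing in the planned output separates the drug's share from the entry rule's share. The version history adds that eotaxin-1 data can be stratified by screening level to assess the treatment effect. For raw change, that would concentrate the artefact in the highest stratum.

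The second matter is precision. With at most 42 subjects in a 2:1 ratio (28 and 14), a raw change score brings baseline noise into any comparison of arms. The screening value needed to remove it is already collected.

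**Working it through.** There is no figure in the plan to reproduce: Protocol 8.2 gives no SD, correlation or effect behind the sample size, and no document gives the share of candidates below 50 pg/mg.

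**Inputs.** From the documents: the gate, the shared baseline, and 28 versus 14 subjects. Assumed: *q*, the share screened out by the threshold; *r*, the correlation between screening and Day 56 log values among unselected candidates; *s*, their SD on the log scale; normality; and no true change over time.

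**1. Expected fall without drug effect.** With c the *q*-quantile of the standard normal and λ = φ(c)/(1−q), the expected fall is (1−r)·λ SDs. The geometric mean falls by 1 − exp(−(1−r)·λ·s).

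| q | r | s | λ | Fall, SDs | Fall, % |
|---|---|---|---|---|---|
| 0.10 | 0.8 | 0.5 | 0.195 | 0.2 × 0.195 = 0.039 | 2 |
| 0.30 | 0.6 | 0.8 | 0.497 | 0.4 × 0.497 = 0.199 | 15 |
| 0.50 | 0.4 | 1.0 | 0.798 | 0.6 × 0.798 = 0.479 | 38 |

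The first and last rows are the extremes over q 0.10-0.50, r 0.4-0.8 and s 0.5-1.0. With q = 0.05 and r = 0.7-0.9 the fall is only 0.01-0.03 SD.

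**2. Is the comparison of arms biased?** Simulation with 28 versus 14, no drug effect, 20,000 runs per setting, q from 0 to 0.5 and r from 0.3 to 0.9: the mean difference in change between arms stayed within 0.005 SD of zero, and a two-sided test at 0.10 rejected in 9.7-10.4% of runs. There is no bias.

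**3. Is the within-arm change misleading?** In the same simulations, a test of the arm's own change against zero at nominal 0.10 rejected in 10-31% of runs (active) and 10-20% (placebo) with 5-20% screened out. With 50% screened out the figures were 25-87% and 17-60%. The SAP plans no such test; the rates show how often a descriptive fall would look convincing. The larger arm looks convincing more often simply because it is larger.

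**4. Precision for tissue eotaxin-1.** Let V be the variance of the screening value after truncation, V = 1 + cλ − λ². In units of the unselected variance, change has variance (1−r)²V + (1−r²), and the baseline-adjusted value has 1−r². At q = 0.30, c = −0.524 and V = 1 − 0.260 − 0.247 = 0.493.

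- r = 0.3: 0.91 / (0.49 × 0.493 + 0.91) = 0.91/1.151 = 0.79; interval narrower by 1 − √0.79 = 11%.
- r = 0.6: 0.64 / (0.16 × 0.493 + 0.64) = 0.64/0.719 = 0.89; narrower by 6%.

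In sample-size terms, 1/0.89 to 1/0.79 is about 12-27% more subjects.

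**5. Precision for UCEIS.** Without truncation V = 1 and the ratio reduces to (1+r)/2: 0.65 at r = 0.3 and 0.80 at r = 0.6. This is the best case. Simulated at 28 versus 14, where the slope must be estimated, it was 0.67 at r = 0.3 and 0.77 at r = 0.5 (formula 0.75).

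**The case against.** The strongest reply is that the placebo arm exists to deal with this. The entry rule acts before randomisation, its expected effect is equal in both arms, and any difference between arms removes it. The placebo-corrected mean in the synopsis would therefore be enough to cure the artefact; ANCOVA adds precision, not validity. All of that stands. A reader might infer that the arm comparison itself is biased, and it is not. What remains is that the SAP does not plan that comparison for tissue eotaxin-1.

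A reader might also infer that both arms are bound to show a fall. The documents do not support that. The size depends on three unstated quantities, and two design features limit sampling noise: eotaxin-1 is measured on two biopsy samples, and Day 56 tissue comes from the same region as at screening. In arms of 28 and 14 a small expected fall may not be visible.

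It is tempting to say that UCEIS has the same structure. It does not: UCEIS is not an entry criterion. The Mayo endoscopic sub-score of 2 or more is, so any regression in UCEIS is indirect, and nothing here sizes it. Tissue eosinophil count has no threshold either. Nor does (1+r)/2 apply to tissue eotaxin-1, because it ignores the truncation that creates the problem.

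Finally, the trial is exploratory, its analyses are descriptive, PD is a secondary objective, and Protocol 8.3.4 allows further exploratory analyses. Raw change in a descriptive table is not an error. But an unspecified later analysis does not replace a planned one, least of all for the marker that speaks most directly to mechanism.

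**Conclusion.** The point holds with limits. One biopsy reading serves as gate and baseline, so some fall in tissue eotaxin-1 is expected in each arm without drug effect. Under the assumed ranges it is about 2-38%; it could be negligible. The defect is that the SAP leaves the within-arm change as the only planned readout and drops the placebo-corrected summary promised in the synopsis.

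Baseline adjustment is a further improvement. For tissue eotaxin-1 the variance ratio is about 0.79-0.89 if 30% are screened out and r is 0.3-0.6. For UCEIS it is at best 0.65-0.80 over the same correlations, a missed gain. Every magnitude rests on assumed inputs; the direction needs only that the threshold excludes someone and that r is below 1.

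**What to change.** - In SAP 9.4.2 (UCEIS) and 9.4.4 (tissue eotaxin-1, and maximum and mean tissue eosinophil count), add a between-arm estimate with confidence interval from an ANCOVA of the Day 56 value on treatment, screening value and prior anti-TNF stratum. Use the log scale for the tissue markers, report ratios, and say beforehand how zero counts are handled.
- Keep the per-arm descriptive tables.
- State beside the tissue eotaxin-1 tables that change within an arm is not evidence of drug effect, because the marker was used to select subjects.

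The cost is a few sentences in the SAP and a degree of freedom for each added covariate. No new data are needed: screening values and anti-TNF history are already collected.
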